#### Ecological momentary assessment. Participants will complete EMA

using their smartphone during the 1-week baseline, and during the first and final weeks of study cigarette use. As in our prior research, the MetricWire application platform will be used for acquiring both prompted and smoking-initiated assessments. Prompted assessments: Participants will specify their typically wakeful hours at screening. They will be prompted 5 times daily at random intervals averaging 150 minutes in length. Participants will be asked to indicate how recently they have smoked (1 item), whether this was a study or non-study cigarette (1 item), and whether they are about to smoke (1 item). Participants will then be asked to rate their current urge to smoke (1-item), negative affect (4 to 6 items), positive affect (2 to 4 items), and pain (2 to 4-items; see examples in Table 2). Responses will be on a 9-point scale ranging from "not at all" to "extremely." Participants can delay responding for a brief period of time (e.g., 15 minutes), after which the response will be coded as missing. Smoking-initiated assessments: Participants will be prompted three times each day to indicate the next time they are about to smoke; participants will then respond to a similar set of items as in the prompted assessments before and/or after smoking the cigarette. End of day/Morning assessments: Throughout study cigarette use, participants will be prompted at the end of the day to report how many cigarettes they smoked that day, how many were usual brand versus study cigarettes, and any occasions of non-cigarette tobacco use. Participants will also be asked to rate their severity of withdrawal symptoms over the past 24 hours and the quality of their sleep the night before. If needed, this assessment may be prompted the following morning for participants to report on the prior day. Compensation. Participants will be compensated \$5 per day for completing at least 4 prompted assessments. Participants will earn an additional \$50 per week for completing 4 out of 5 prompted assessments and the end of day/morning assessment every day. This reinforcement schedule is consistent with that used previously in our lab, which has yielded an 88% completion rate.

Carbon Monoxide Breath Testing: Participants will be asked to inhale and hold their breath for 15 seconds, and then exhale into a commercially available breath CO monitor (e.g., Covita Smokerlyzer). This device is fitted with a disposable mouthpiece and cleaned thoroughly between participants. Given that this test requires participants to remove their mask, face to face contact will be minimized during this test under COVID restrictions. Participants will be instructed how to self-administer the test, which they will then

complete alone in a room with closed door or outside in a private, designated area. Participants will be observed completing the test via Zoom video (when indoors) or through the glass door to the designated outdoor area.

Questionnaires: A standard battery of questionnaires and interview measures will be administered via Redcap to evaluate psychological, behavioral, smoking, pain and health information. These will include: demographics, a Tobacco Use History interview, a Brief Medical History questionnaire and Follow-up Form, a Medication Changes Ouestionnaire, a Health Changes Ouestionnaire, a Drug Use History guestionnaire, a Motivation to Quit Smoking questionnaire, the Alcohol Use Disorders Identification Test (AUDIT), the Fagerstrom Test of Cigarette Dependence (FTCD), the Wisconsin Inventory of Smoking Dependence Motives (WISDM), the Minnesota Tobacco Withdrawal Scale (MTWS), the Questionnaire of Smoking Urges-Brief (QSU-B), the Brief Pain Inventory-Short Form (BPI-SF), the Graded Chronic Pain Scale (GCPS), the Pain and Smoking Inventory (PSI), the Smoking Self-Efficacy Questionnaire (SEQ-12), the Center for Epidemiological Studies-Depression scale (CES-D), and a follow-up Quitting Behaviors questionnaire. Additional questionnaires may also be used, including: the Pain Catastrophizing Scale (PCS), a Smoking Cessation Therapy Use questionnaire, the Life Events Checklist (LEC), a measure of Adverse Childhood Events (ACES), Composite Morningness Scale (CMS), PROMIS Sleep Questionnaire, the Distress Tolerance Scale (DTS), and Profile of Mood States (POMS), State-Trait Anxiety Inventory (STAI), Snaith-Hamilton Pleasure Scale (SHAPS), and the Positive and Negative Affect Schedule (PANAS), the Chronic Pain Self-Efficacy Scale (CPSS), the Cigarette Evaluation Scale (CES), PATH Dependence Scale, Cigarette Expectancies (Study Cigarette & Usual Brand) Scale, Study Cigarette Purchase Task; Perceived Health Risk (Study Cigarettes & Usual Brand), Coping Strategies Questionnaire-short form, CSQ-7 item, Chronic Pain Coping Inventory (CPCI), Pain Anxiety Symptom Scale (PASS-20), and the CHOIR body map.

Standardized Tests of Psychiatric and Cognitive Functioning. The M.I.N.I. is a structured interview of psychiatric functioning, and will be administered by trained research staff under the supervision of the PI. In addition, the Wide Range Achievement Test (WRAT-4) word reading test is a standardized measure that requires approximately a minute to administer. Participants are asked to read aloud from a page of increasingly difficult words, and to say the words as smoothly as possible. A standardized score can be calculated and provides an approximate index of current reading level/cognitive ability. This measure will allow us to set a minimum threshold necessary to ensure that participants can read and understand all study-related procedures.

### **Selection of Subjects**

• List inclusion/exclusion criteria and how subjects will be identified.

### Inclusion Criteria

- diagnosis of non-cancer chronic (>3 months) back pain (confirmed in medical record or by provider):
- Pain duration of ≥ 3 months with EITHER an average intensity of ≥ 4/10 OR worst pain average of ≥ 6/10 as assessed by the Graded Chronic Pain Scale (GCPS);
- 21-70 years of age;
- daily smoking at least > 2 years lifetime;
- smoking at least 7 cigs/day for the past 6 months, with no continuous periods of abstinence > 2
   weeks:
- expired breath CO concentration > 10 ppm to confirm reported smoking status;
- intact intellectual functioning as indicated by score of ≥ 80 on the WRAT-4 word reading subtest;
- have an iPhone or Android smartphone capable of running the EMA software;

### Exclusion criteria

- actively taking steps to quit smoking;
- inability to attend all required experimental sessions;
- report of significant health problems including but not restricted to untreated chronic hypertension, emphysema, seizure disorder, history of significant heart problems;
- systolic blood pressure > 160 or diastolic blood pressure > 100 (participants failing for blood pressure will be allowed to rescreen once);
- resting heart rate > 100 (participants failing for heart rate will be allowed to rescreen once);
- breath alcohol level > 0.000 (participants failing for BAL will be allowed to rescreen once);
- current use of prescription opioid pain relievers;
- lifetime history of bipolar or psychotic disorder;
- current unstable psychiatric disorder as assessed by the MINI;

- suicidal ideation with plan or intent; potential subjects who endorse items 4 (Active Suicidal
  Ideation with Some Intent to Act, without Specific Plan) and/or 5 (Active Suicidal Ideation with
  Specific Plan and Intent) on the Columbia Suicide Severity Rating Scale will be excluded from study
  participation, and referred to appropriate psychiatric treatment;
- use of non-cigarette tobacco products or electronic cigarettes > 8 times in past 30 days;
- current use of nicotine replacement therapy (NRT) or other smoking cessation strategy;
- use of Spectrum investigational cigarettes or low nicotine content cigarettes in the past year;
- quit attempt in the past 30 days resulting in greater than 3 days abstinence;
- past year alcohol or substance use disorder;
- use of illegal drugs as measured by urine drug screen (other than marijuana);
- daily or near-daily use of cannabis;
- primary pain complaint was due to specific medical conditions (e.g., cancer, rheumatoid arthritis, or complex regional pain syndrome);
- spine surgery within the past year or planned surgery within the timeframe of the study;
- positive pregnancy test among women

Changes to inclusion criteria made to reflect changes in criteria surrounding pain rating, now incorporating worst pain rating.

# **Subject Recruitment and Compensation**

Describe recruitment procedures, including who will introduce the study to potential subjects. Describe
how you will ensure that subject selection is equitable and all relevant demographic groups have access
to study participation (per 45 CFR 46.111(a) (3)). Include information about approximately how many
DUHS subjects will be recruited. If subjects are to be compensated, provide specific prorated amounts
to be provided for expenses such as travel and/or lost wages, and/or for inducement to participate.

Subjects will be recruited through responses to advertisements, invitations within the Duke patient EHR portal, or by being contacted by study staff because they previously participated in an experiment within the lab and indicated they were willing to be contacted again in the future.

Duke MyChart: Potential participants will be recruited through referrals through the patient EHR portal (Duke MyChart). Patients with recent medical visits meeting pre-specified eligibility criteria will receive an invitation for study participation through MyChart or by email. Importantly, data from the Duke EHR indicates that over 1,500 smokers sought treatment for non-cancer chronic pain within the Duke Health system within the past year. As in previous studies in our lab, patients responding to the invitation will be contacted by study staff to complete a phone screen or will be invited to complete the initial online web screener.

Working with DOCR Maestro Care Analysts (MCAs), we will develop a computable phenotype that will allow us to identify potentially eligible patients. The DOCR MCAs will send us a list of potentially eligible patients. We will then verify the potential eligibility of those patients with manual chart reviews. We will then return an updated list of potentially eligible patients to the MCAs so they can send the MyChart Research Message out to those patients we have verified may be eligible. For those recipients of the MyChart Recruitment Message who do not open/view the message, we will send reminder emails, texts, or calls up to 2 times based on the patient's preferred method of contact. We may decide to remove the initial MyChart Recruitment Message and exclusively use direct-to-patient phone calls, texts, or emails to potentially eligible patients if the MyChart Message is unsuccessful in gaining participant interest. We confirm that we are checking against the "banner" in MaestroCare to verify whether or not the patient has opted out for being contacted.

Advertisements: We will advertise in local print media, on the internet (e.g., banner ads, craigslist), social media (e.g., Facebook, snapchat, twitter), and posted flyers. Participants responding to advertisements will be provided with a study phone number to contact the lab to learn more about the study and complete an initial phone screen. Advertisements will also include a link to a secure online REDCap survey if they prefer to compete preliminary screening questions online.

Contact Repositories: Participants may also be recruited through their involvement in the "CfAST Study Contact Repository" (Pro00088653). This secure REDCap database includes contact information for individuals who have previously participated in CfAST studies and have agreed to be contacted for future research.

When we receive calls from potential subjects we will return their call and ask information including name, address, age, smoking history, and questions about pain. They will be given a brief description of our studies and will be asked questions to determine interest and eligibility. Individuals will be asked if they

would like their screening information stored in a database for future studies for which they may be potentially eligible or destroyed after completion of the study. If they do qualify we will schedule a screening session where we will follow all IRB protocols of informed consent.

#### Compensation:

Participants are compensated for the time and effort they dedicate to the study procedures. They will receive \$30 for the initial screening visit, \$50 for completing the initial abstinence/training session, \$30 for each of the weekly visits, and \$50 for the second abstinence session. In addition, participants can earn a \$100 completion bonus for attending all sessions, up to \$255 for completing EMA, and up to \$600 bonus for biochemical verification of adherence to study cigarettes (\$1235 total). Thus, compensation is provided not only for repeated laboratory visits, but also for use of study cigarettes and completion of EMA. EMA requires multiple responses throughout the day, for a period of 3 weeks, and compensation greatly improves participants' willingness to complete these repeated assessments. In addition, study cigarette use requires committed ongoing effort from participants for a period of several weeks. As such, the compensation is commensurate with the time and effort involved. The \$100 completion incentive is included because high attrition will reduce the statistical power of the study. In addition, the \$600 adherence bonus (or \$200 if participants truthfully disclose non-study cigarette use) is included to maximize compliance with study product because non-study cigarette use will compromise the ability to evaluate group differences. Compensation will be provided at each visit and weekly for EMA. Participants are free to discontinue at any time and will receive compensation for the sessions that they complete at the same rate as participants who complete the study.

#### **Consent Process**

• Complete the consent section in the iRIS Submission Form.

# **Subject's Capacity to Give Legally Effective Consent**

• If subjects who do not have the capacity to give legally effective consent are included, describe how diminished capacity will be assessed. Will a periodic reassessment occur? If so, when? Will the subject be consented if the decisional capacity improves?

We do not include participants who cannot read/write/understand English or those who do not have the capacity to give legal consent.

### **Risk/Benefit Assessment**

• Include a thorough description of how risks and discomforts will be minimized (per 45 CFR 46.111(a) (1 and 2)). Consider physical, psychological, legal, economic and social risks as applicable. If vulnerable populations are to be included (such as children, pregnant individuals, imprisoned persons or cognitively impaired adults), what special precautions will be used to minimize risks to these subjects? Also identify what available alternatives the person has if he/she chooses not to participate in the study. Describe the possible benefits to the subject. What is the importance of the knowledge expected to result from the research?

Potential Risks: Continuing to smoke carries significant health risks. Participants enrolling in this study are not attempting to quit smoking, and will not be provided with smoking cessation treatment. However, participants will be provided with referral information for smoking cessation at the conclusion of the study. Use of VLNCs provided during the study does not pose any reduced risk relative to typical combustible cigarettes. There is a risk that participants in the VLNC condition could increase their smoking to compensate for lack of nicotine. Although infrequent, use of study cigarettes may also contribute to other adverse effects, including throat irritation, coughing, or nausea. There is also the risk that smokers assigned to the VLNC condition will experience increased withdrawal symptoms, including increased pain or negative affect due to decreased nicotine intake. All participants will be advised of potential symptoms and provided with coping strategies and support as necessary. Subjects may also experience withdrawal symptoms during 24-hr abstinence period. Finally, there is a risk attendant to the confidentiality of psychological data and self-report data.

There are no direct benefits to participants, but the study will increase knowledge of the role of nicotine and non-nicotine factors in the comorbidity between smoking and pain, and the effects of VLNCs on clinically-relevant outcomes among smokers with chronic pain. This information will aid in the development and evaluation of new and more effective treatments for smokers with pain. Given minimal risks of participation, we consider the risk/benefit ratio acceptable and representing an appropriate level of risk for human participation. Steps taken to minimize risks to participants are described below.

Breach of Confidentiality. Participants will be assigned a unique subject ID that will be used on all research materials. The only link between the assigned unique ID and identifiable information will be stored in the enrollment log on a Duke School of Medicine password-protected server. All forms with identifiable information including the study consent forms will be stored in a locked file cabinet in a separate location from the study data. De-identified study materials will be maintained in participant binders in a locked suite of the CfAST lab space, or for electronic data, on a secure password-protected Duke School of Medicine server. All information collected as part of this study will be accessible only to research staff. Interviews with participants will be conducted in private rooms. Biological samples for drug and pregnancy tests will only be labeled with the participant's ID. Many subjective measures will be administered via a secure Redcap surveys. EMA assessments will be administered via a secure platform (MetricWire). These will also be identified by participant ID, which will be entered into the computer prior to subject data entry. Biological markers of nicotine exposure will be marked with participant ID, date and session number and stored in a -80 freezer that is locked within the laboratory suite. No information will be shared with participants' clinicians unless the participant requests this in writing. All investigators and staff have undergone (and any new staff will undergo) human subjects' ethics training and are fully conversant with ethical principles around confidentiality. Assessments, consenting and study procedures will be closely supervised by the Pl.

Nicotine Withdrawal/Treatment Referral. Participants will be fully informed at the start of the study about potential risks, including symptoms of nicotine withdrawal and risks of continued tobacco use. Participants who are seeking treatment for smoking cessation are not eligible to participate. Information regarding smoking cessation treatment resources and appropriate referrals will be provided to all participants who consent but do not pass screening for any reason. In addition, smoking cessation treatment information will be provided at the conclusion of the study for any individuals interested in quitting at that time.

Increased Smoking of Study Cigarettes. Past two-week timeline follow-back assessed at V1 will be used to establish a baseline average of usual brand cigarettes smoked per day. Past-week timeline follow-back will be reassessed at each subsequent weekly visit, and changes in total cigarettes smoked per day relative to

baseline will be calculated. As with our prior studies utilizing investigational cigarettes, participants exhibiting  $\geq 200\%$  increase in smoking rate will be removed from the study to prevent increased toxicant exposure.

Protection of pregnant women and fetuses. Sexually active females who are not pregnant must agree to use appropriate contraception during the course of the study, and to notify the study physician if they become pregnant during the study. A urine pregnancy test will be conducted during screening and must be negative for participants to continue with the study. A second urine pregnancy test will be conducted at visit 1, prior to dispensing any study cigarettes. As such, two sequential negative pregnancy tests are required before any study cigarette administration.

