Baseline Abstinence/Training Session. Following screening, participants will complete a baseline abstinence challenge session, in which they are asked to abstain from smoking for 24 hours prior to the session. Expired CO < 6 ppm or 50% reduction from baseline will be used to verify abstinence. Participants will complete measures of craving, pain, and withdrawal. At the conclusion of the session, Metric Wire software will be installed on their smartphone, and they will be trained in the procedures for EMA.

Weekly Sessions. After one week of baseline EMA while smoking of usual brand cigarettes, participants attend an in-person visit (V1), during which they will be randomized to NNC or VLNC condition, given a supply of study cigarettes, and provided with a schedule of 4 weekly follow-up visits (V2 through V5). During each of the weekly visits participants will complete self-report measures and a timeline follow-back of past-week smoking, other tobacco use and alcohol/substance use; additional study cigarettes will be supplied; and breath CO and urinary measures of nicotine exposure will be collected. Adverse events will be monitored, as well as changes in medical history including new or discontinued medications, new treatments for current medical problems, or other study participation.

Post-Intervention Abstinence Session. Immediately following the final weekly visit, participants will be asked to abstain from smoking for 24 hours prior to attending a final laboratory abstinence session. Procedures and measures will be identical to those used in the initial abstinence session.

Follow-Up 3-Month Phone Call. Participants will be contacted by phone 3 months after completing the study to provide information about current smoking, recent quit attempts, and cessation strategies used.

Table 1. Schedule of Events and Procedures

CIGARETTES		UB	NNC	NNC or VLNC Cigarettes							
REMOTE ASSESSMENT		EMA			E			EMA			
IN-PERSON VISITS	Screening	24hr / Test 1 Traini (A1)	./ ng	Visit Week 1 (V1)	Visit Week 2 (V2)	Visit Week 3 (V3)	Visit Week 4 (V4)	Visi We 5 (V5	ek A	ABS Test 2 A2)	
Study Day	-30 to -1	0		7	14	21	28	35	3	36	
Window (in days)		0		(± 2)	(± 2)	(± 2)	(± 2)	) (±	2) (	± 1)	
PROCEDURES					-						
Informed Consent	Х								Î		
Eligibility	Х										
Demographics	Х										
Medical History	Х										
Tobacco History	Х										
Breath CO Sample	Х	Х		X	Х	Х	Х	Х	>	(	
Breath Alcohol	Х	Х		X	Х	Х	Х	Х	>	(	
Urine Drug Screen	х										

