# **Data Analysis & Statistical Considerations**

Describe endpoints and power calculations. Provide a detailed description of how study data will be
analyzed, including statistical methods used, and how ineligible subjects will be handled and which
subjects will be included for analysis. Include planned sample size justification. Provide estimated time
to target accrual and accrual rate. Describe interim analysis including plans to stop accrual during
monitoring. Phase I studies, include dose escalation schema and criteria for dose escalation with
definition of MTD and DLT.

Hypothesis testing will be conducted using generalized mixed models, which are well-equipped to handle missing data, even when data is missing not completely at random. Multiple imputation will also be used to further address potential bias resulting from missing data.

Specific Aim 1 will examine the effects of NNCs versus VLNCs on: a) changes in cigarettes smoked per day, nicotine dependence, withdrawal symptoms and pain across the 5 weekly visits (V1 through V5), and b) pre-post intervention changes in withdrawal and pain following 24hr abstinence. For both sets of models, Group will be entered as a between-subjects factor with 2 levels (NNC or VLNC), and Session will be included as a within-subjects factor with 5 (week) or 2 (pre- vs post-intervention) levels. Baseline pain and FTCD scores, assessed at screening, will be included along with sex as covariates. We predict that the VLNC group will exhibit decreasing nicotine dependence and smoking frequency across the 4 weeks of study cigarette use, with no change for the NNC group (i.e., Group x Week interactions). Based on our prior work, we predict only a minimal increase in withdrawal during the first week of VLNC use, with no group differences in withdrawal or pain during remaining weekly visits. During 24-hr abstinence, we predict a Group x Session interaction, such that the VLNC group will exhibit pre- to post-intervention decre ases in withdrawal and pain, with no change for the NNC group. Secondary analyses will evaluate effects of abstinence, controlling for weekly changes during ad lib smoking, by including withdrawal and pain assessed at V1 (pre-intervention) and V5 (post-intervention) as time-varying covariates.

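### The V2–V5 follow-back always recalls seven days, but the visit windows allow 3 to 11 days between visits, so cigarettes per day at V2 can include up to 4 usual-brand days or omit up to 4 study-cigarette days

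*Combined protocol and SAP*

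**What the plan says.** Design & Procedures (Weekly Sessions) has participants complete at each weekly visit "a timeline follow-back of past-week smoking, other tobacco use and alcohol/substance use". Risk/Benefit Assessment (Increased Smoking of Study Cigarettes) sets the baseline differently: "Past two-week timeline follow-back assessed at V1 will be used to establish a baseline average of usual brand cigarettes smoked per day". For later visits it says "Past-week timeline follow-back will be reassessed at each subsequent weekly visit", and from this it calculates "changes in total cigarettes smoked per day relative to" baseline.

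Table 1 counts study days from the first abstinence session (day 0). V1 to V5 fall on days 7, 14, 21, 28 and 35, each with a window of ± 2 days. Participants smoke their usual brand until V1, when they are randomised and first supplied with study cigarettes.

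Data Analysis & Statistical Considerations (Specific Aim 1) models "changes in cigarettes smoked per day, nicotine dependence, withdrawal symptoms and pain across the 5 weekly visits (V1 through V5"), with Session as a five-level factor. It does not name the source of cigarettes per day. The timeline follow-back is the only cigarette count that Table 1 schedules at all five visits.

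**The concern.** The recall has a fixed length and the interval it is meant to describe does not. No section ties the recall to the date of the previous visit, sets a minimum gap, or excludes days before V1 from the V2 value.

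V2 is the first on-study level for Hypothesis 1a, which predicts falling smoking frequency on VLNC cigarettes and no change on NNC cigarettes. Usual-brand days in the V2 average come from before randomisation, when the arms do not differ by treatment. They pull the V2 contrast towards zero. When the gap exceeds seven days, the V2 value instead leaves out the days just after the switch.

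**Working it through.** **The plan's own figure.** The plan gives no figure for visit gaps or dilution. The number attached to this analysis is power of 90% to 99% for the group by weekly session interaction (N = 48, m = 5 occasions, r = 0.4, d = 0.4 to 0.6). Take f = d/2, λ = f²·N·m/(1 − r), and df = 4 and 184.
- d = 0.4: λ = 0.04 × 240/0.6 = 16, power 90.4%.
- d = 0.6: λ = 0.09 × 240/0.6 = 36, power 99.9%.

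The stated range is reproduced. The windows do not enter that calculation, so it neither supports nor weakens this point.

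**Inputs.** Visit days and ± 2 day windows are from Table 1. The seven-day recall is from Weekly Sessions and Increased Smoking of Study Cigarettes. The start of study cigarettes at V1 is from Weekly Sessions and Study Interventions. The day of V1 is counted as a study-cigarette day.

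**Formulas.**
- Gap = 7 + (later offset − earlier offset), offsets −2 to +2. Range: 7 − 4 = 3 to 7 + 4 = 11 days, for every consecutive pair.
- Usual-brand days in the V2 recall = max(0, 7 − gap).
- Study-cigarette days left out = max(0, gap − 7).

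**Extremes at V2.**
- V1 on day 9, V2 on day 12: the recall covers days 5–11, and days 5–8 are usual brand (4 of 7).
- V1 on day 5, V2 on day 16: the recall covers days 9–15, and study-cigarette days 5–8 are left out (4 of 11).

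**All 25 in-window V1/V2 pairs.**

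| Gap (days) | 3 | 4 | 5 | 6 | 7 | 8 | 9 | 10 | 11 |
|---|---|---|---|---|---|---|---|---|---|
| Pairs | 1 | 2 | 3 | 4 | 5 | 4 | 3 | 2 | 1 |

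Ten pairs are shorter than seven days, ten are longer, and five are exactly seven.

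**Size of the dilution.** With c usual-brand days and a steady daily change after the switch, V2 shows (7 − c)/7 of that change.
- Extreme, c = 4: 3/7 = 43% is seen and 57% lost, in 1 pair of 25.
- Average, if offsets are independent and evenly spread (assumption): (4×1 + 3×2 + 2×3 + 1×4)/25 = 20/25 = 0.8 days, and 0.8/7 = 11% lost.
- Illustration with assumed values: if 20 per day falls to 15, the extreme V2 value reads (4×20 + 3×15)/7 = 17.9.

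**Later visits.** The earliest V3 (day 19) is 10 days after the latest V1 (day 9), so a seven-day recall at V3, V4 or V5 never reaches before V1. Those visits can recount or skip up to 4 days of study-cigarette smoking.

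**The case against.** The strongest reply is that the data are not lost. The Ecological momentary assessment section prompts an end-of-day count, split by brand, throughout study cigarette use. Study Cigarette Adherence compares daily reports, returned packaging and follow-back. A reader might infer that the first 4 days of an 11-day interval go unobserved. The documents do not support that: those days also fall in the first week of study cigarettes, which is an EMA week. What stands is narrower. No section says the daily counts replace or correct the follow-back, and their coverage in weeks 2 and 3 is unclear because EMA itself runs only in weeks 1 and 4.

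Second, the source of the outcome is inferred, and the seven-day calculation appears in a safety paragraph. A follow-back is normally recorded by day, so an analyst could drop the days before V1. That is fair: the gap is a missing derivation rule, and a rule would close it.

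Third, participants receive their weekly schedule at V1, so V2 may in practice be booked from the actual V1. The plan does not say so. If it were, the V1–V2 gap would be 5 to 9 days and the error at most 2 days. With an even spread the average would be (2 + 1)/5 = 0.6 days, or 0.6/7 = 9%.

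Fourth, a reader might infer that the increased-smoking check is blinded. Tripled smoking for 3 days after 4 baseline days does read (4×1 + 3×3)/7 = 1.86 times baseline at V2. If it continues, however, V3 recalls only post-switch days and shows it, and daily reports are collected meanwhile. The documents support a possible delay in that check and no more.

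**Conclusion.** The mismatch is real and follows directly from Table 1 and the recall wording. Followed as written, the V2 value of cigarettes per day can hold up to 4 usual-brand days or omit up to 4 study-cigarette days.

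The effect is modest. The V2 contrast loses about 11% on average, with 57% as the 1-in-25 extreme. Spread over the four post-switch visits the average is 11%/4, about 3%. The average rests on evenly spread, independent visit offsets and a steady daily change after the switch. The extreme needs only that both visits are in window and that the change is steady. All of this also assumes the follow-back is the source of the outcome, which the plan implies but does not state.

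One might infer a bias towards one arm. The documents do not support that: both arms share the same windows, and the expected effect is dilution. The stated sample size and power are not in question.

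**What to change.** 1. Have the timeline follow-back at V2–V5 run from the previous visit date to the current visit, in place of a fixed past week.
2. In Data Analysis & Statistical Considerations, name the source of cigarettes per day. Define each on-study value as total cigarettes of any brand divided by the days since the previous visit, with no days before V1 at V2. Usual-brand cigarettes smoked after V1 should stay in the total, because leaving them out would condition the outcome on compliance after randomisation.
3. The increased-smoking check in Risk/Benefit Assessment and the supply calculation in Study Interventions use the same past-week recall. Reconcile both with the Table 1 windows. No change to the removal rule is proposed.

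The cost is protocol and form wording, with the same visits and the same interview. Recall lengthens by up to 4 days when a visit is late. Averages will cover 3 to 11 days, so they will differ in precision and in their mix of weekdays and weekends.
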